- Hyaluronic acid and saline are pre-loaded in insulin plastic syringes before injection for patient blinding. The needle is inserted 2-3 mm apical to the tip of the interdental papilla and directed coronally with an angulation of 45° to the long axis of the tooth, and the bevel directed apically. Then, the papilla is lightly moulded in an incisal direction for 1 minute using gauze.
- -In the follow-up phase, patients are recalled after 3,6months the first injection where clinical remeasurement of the black triangles and standardized digital clinical photographs will be retaken.

Postoperative care:

-Patient self-care instructions (Heitz et al. 2004):							
Avoid any hard brushing and trauma to the surgical site for two weeks.							
- Maintain a soft diet to avoid trauma to the surgical site.							
- After 24 hours patients can use warm saline rinses daily							
- Sutures will be removed fourteen days after the surgery.							
- Plaque control will be maintained by chlorohexidine mouth rinse after the surgery.							
12. Outcomes:							

Outcomes	Outcome name	Measuring device	Measuring units
1ry	interdental papilla loss	Photoshop CS5.	mm
outcome	(Decrease of black triangle		
	area) (mm2)		
2nd	Gain in papillary height	UNC Periodontal Probe	
outcomes			mm
	Change in the distance (CP-		
	BC)	Digital periapical radiograph	
		(linear measurement)	mm
	CAL		
		UNC Periodontal Probe	
	Pocket depth (PD)		mm
		UNC Periodontal probe	
	Gingival recession		mm
	(GR)	UNC Periodontal probe	
			mm
	Gingival bleeding		
		UNC Periodontal probe	G: : 1
			Gingival
	Plaque index		bleeding score
		UNC Periodontal probe	Diagna Inday
	Post-surgical patient		Plaque Index
	Satisfaction and post-	Post-surgical patient	score
	injection	satisfaction questionnaire	(1.7) noint 22-1-
		(PSPSQ) (Kiyak, Hohl, West,	(1-7) point scale
		& McNeill, 1984)	

-Digital clinical photographs: (SABT) mm (Abdelraouf et al. 2019)

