Gingival recession will be measured using UNC periodontal probe from the cemento-enamel junction till the gingival margin (Miller, 1985).

Gingival Bleeding score:

- Gingival bleeding score will be performed through gentle probing of the orifice of the gingival crevice from all four surfaces of all teeth using UNC Periodontal probe.
- Recorded as (+) if bleeding is present or (-) if bleeding is absent.
- If bleeding occurs within 10 seconds a positive finding is recorded and the number of positive sites is recorded and then expressed as a percentage of the number of sites examined (*Ainamo & Bay, 1975*).

Patient Satisfaction:

- Three questionnaires will be asked to determine patients' satisfaction with the outcome of surgery
 - 1. Considering this was an elective operation, how likely would you be to recommend it to others?
 - 2. If you had to make the decision again, how likely would you be to undergo this surgery'?
 - 3. Considering everything, how satisfied are you with the outcome of your surgery
- These questions could all be answered by the patient using a 7-point response scale where: Very Satisfied = 7; Not At All Satisfied = 1. (*Kiyak et al., 1984*).

13. Participant timeline

13.	T0	T1	T2	T3	T4	T5	1-
Participant			(Surgical	Starting	3-	6-	
timelineTime			phase- 8	from T2	months	months	
point			weeks)	till 7th	post-	post-	
				day	surgical	surgical	
Enrollment	X						
Eligibility	X						
screen							
Informed	X						
consent							
Initial phase		X					
(Oral hygiene							
measures)							
standardized							
periapical							
radiograph							
study casts	X					X	
Allocation			X				
Intervention							
Injection			X				
Surgical tube							
technique							
Post-operative				X			
Care							
Papillary		X	X		X	X	
height, CAL,							
PD, GR							
measurements							

SABT					
Patient		X		X	
Satisfaction					

14. Sample size:

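### The three satisfaction items are worded for surgery although the outcome also covers the injection arm, so the two arms cannot be relied on to answer the same question

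*Protocol*

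**What the plan says.** Protocol section 12 lists satisfaction among the secondary outcomes. The table row names both groups of patients: it opens "Post-surgical patient", continues "Satisfaction and post" and ends with injection. One instrument and one 1 to 7 scale serve both.

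The Patient Satisfaction text in the same section introduces the items with "Three questionnaires will be asked to determine patients' satisfaction with the outcome of surgery" and then prints three of them. The last, which asks for an overall judgement, is worded "Considering everything, how satisfied are you with the outcome of your surgery". The one placed first concerns advice to other people and is worded "Considering this was an elective operation, how likely would you be to recommend it to others". Between these two stands the item on choosing the same course again, worded "If you had to make the decision again, how likely would you be to undergo this surgery".

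For every item the reply is given on one "7-point response scale where: Very Satisfied = 7; Not At All Satisfied = 1". No second version is given for injected patients.

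The Comparator paragraph before section 7 describes hyaluronic acid as a non-surgical injection. Section 17 states that participants are not blinded. Section 16a allocates patients 1:1.

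**The concern.** A satisfaction score compares two treatments only if patients in both arms rate the same thing. Here a patient in the tube arm is asked about the operation just performed. A patient in the control arm has had a course of injections, knows it, and is asked about an operation.

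The ambiguity exists in one arm only, so it is tied to treatment and does not average out like random noise. If staff explain the items aloud to control patients alone, the arms again answer different questions.

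What is at stake is a secondary outcome, but it is the only patient-reported one in the section 12 table. The patient's own view carries weight when a graft operation is compared with an injection, and the protocol's rationale argues for non-surgical treatment partly on patient comfort.

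**Working it through.** No arithmetic applies, because the protocol gives no effect size, standard deviation or sample size for satisfaction. The check sets the items beside the arms and the anchors.

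**Step 1: what each item names and asks**

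| Item | Treatment named | Question asked | Do the stated anchors fit? |
|---|---|---|---|
| 1 (recommend to others) | an operation | how likely | No |
| 2 (decide again) | surgery | how likely | No |
| 3 (overall) | the patient's surgery | how satisfied | Yes |

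Three of three items name an operation or surgery. Two of three ask about likelihood, while the scale is labelled "Very Satisfied = 7; Not At All Satisfied = 1".

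**Step 2: who is asked.** The table row covers both arms, so injected patients are meant to answer. With 1:1 allocation they are about half of the patients.

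**Step 3: how a control patient could read each item**

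- Item 2 is the clearest case. Section 11 has the study explained to every patient, so a control patient knows that the alternative was surgery. Take a patient who is pleased with the injections and would choose them again. If the item is read as the treatment received, the answer is near 7. If it is read as the tube operation, the same opinion may give an answer near 1. A tube patient has only the first reading.
- Item 1 has the same ambiguity, because what is to be recommended is described as an operation.
- Item 3 is the mildest case. It speaks of the patient's own surgery, so a control patient will probably apply it to the injections or leave it blank.

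**Step 4: could blinding remove the ambiguity?** No. The Group B procedure in section 11 mentions pre-loaded syringes for patient blinding, but section 17 says participant blinding does not apply. A patient would in any case not mistake injections for a graft operation.

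**Step 5: the anchors.** The mismatch on items 1 and 2 is identical in both arms. It leaves the meaning of a score on those items unclear, but it does not by itself push the arms apart. It is a second, separate defect.

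**Step 6: what is not touched.** The sample size in section 14 rests on black triangle area (difference 1 mm², SD 0.74 mm², 80% power, 10 sites per group before drop-out). None of these inputs involves satisfaction.

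**The case against.** The strongest reply is that the protocol itself uses surgical language for both arms. Section 16b refers to both treatments as surgical procedures. The section 13 timeline places the injection in the surgical phase and labels the follow-up visits post-surgical for everyone. In that usage the patient's surgery simply means the treatment received, and a control patient can answer. This stands against one tempting inference, that injected patients cannot answer the items at all. It does not remove the point: the Comparator paragraph calls the control non-surgical, so the usage is inconsistent, and how investigators use a word does not settle how a patient reads it.

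A reader might also infer that the between-arm comparison is invalid. The documents do not support that. Section 20 covers the primary outcome only, no test of satisfaction is stated, and the list of secondary outcomes in section 7 omits it. A comparison is implied by its place in the section 12 table of a two-arm superiority trial. A statistical analysis plan may say more, but it would not change the words put to patients.

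A reader might infer that the satisfaction scale is what separates the arms. It is not: it fits item 3 and misfits items 1 and 2 equally in both arms.

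Nor is a timing difference shown. The section 13 timeline has a single satisfaction row for all patients; its columns are partly broken in the text available, and no arm-specific timing appears.

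Two uncertainties remain. The cited questionnaire and the form handed to patients are not shown, so item-specific anchors may exist there. Section 26 has the consent forms translated into Arabic and is silent on the questionnaire, so the English wording may not be what patients read. Both limit how firmly the anchor point can be pressed. The protocol nevertheless prints one item set and one pair of anchors, and followed as printed they have the defects described.

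**Conclusion.** The concern holds in a limited form. As printed, the items cannot be relied on to measure the same thing in both arms, and a difference on this secondary outcome could partly reflect wording. The extent is all three items in the control arm, about half of the patients, with item 2 most exposed and item 3 least. The direction and size of any distortion cannot be derived from the protocol.

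The anchor mismatch on items 1 and 2 is a separate scoring defect that affects both arms alike.

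The conclusion assumes that patients receive the items and anchors as section 12 prints them, and that the arms will be compared on satisfaction. It is a minor point that is worth correcting because the correction is cheap and answers already given to ambiguous questions cannot be repaired afterwards.

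**What to change.** In section 12, Patient Satisfaction:

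- Use *the treatment you received* in place of operation and surgery in all three items, with identical wording in both arms, and adjust the introductory sentence to match.
- Give items 1 and 2 likelihood anchors: 1 = not at all likely, 7 = very likely.
- Keep the satisfaction anchors for item 3.
- Carry the same wording into any translated form that patients complete.
- State in the protocol and the report that the cited questionnaire was adapted.

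The work is three reworded sentences and one added pair of anchors. The real cost is that all three items then depart from the cited instrument, so scores are less directly comparable with other results obtained with its wording. If patients have already answered the present items, the change should go through the amendment procedure in section 25, and the report should say which version each patient answered.

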It is a minimally invasive non-surgical injection of hyaluronic acid that observed to overcome the major limiting factor in most surgical techniques regarding the limited blood supply and the small working space. Supported by a recent study conducted by *Jinng etal.* 2019, who reported significant increase in the height of the gingival papilla and reduction of the area of the black triangle between baseline and 3 or 6 months in a group with thick gingival biotype after injection with hyaluronic acid, that was adding possible maximum effect with minimal postoperative hazards.

II.B. Objectives of the study:

7. Aim of the study

The aim of this randomized clinical trial is to compare the clinical effect of surgical Tube technique versus Hyaluronic Acid gel injection in reconstruction of the interproximal papilla in patients with class II papillary defect.

Picots:

P: Population: patients with class II papillary defect.

I: Intervention: Tube technique hosting sub-epithelial connective tissue graft.

C: Control: Hyaluronic acid injection.

Primary outcome: interdental papilla loss (Decrease of black triangle) (mm2)

Secondary outcome: assessment of gain in papillary height, radiographic distance between (CP-

BC), assessment of CAL. PD reduction, amount of gingival recession.

T: Time frame: 6 months.

S: Study design: Randomized clinical trial.

Hypothesis:

Null hypothesis: There is no difference in the gain in papillary height comparing hyaluronic acid injection versus Tube technique in patients with class II papillary defect.

8.Trial design

The study is designed as a superiority, 2 arm parallel groups, randomized clinical trial with allocation ratio 1:1.

III. Methods

A) Participants, interventions and outcomes

9. Study settings:

This study will be carried out on patients enrolled from the outpatient and postgraduate clinics of Oral Medicine and Periodontology department, Faculty of Dentistry, Cairo University.

10. Eligibility criteria:

Inclusion Criteria:

- Highly motivated patients with papillary deficiency types II, according to *Nordland* and *Tarnow 1998* classification will be selected, having at least one deficient papilla in the anterior region.
- Distance between the contact point and inter-proximal bone crest (CP-BC) of ≤ 7 mm and probing depth of ≤ 4 mm at the deficient papillary site (*Abdelraouf etal. 2019*).
 - Patients with full mouth plaque index (PI) and gingival index (GI) scores should be between 0-1.

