 - Healthy patients free of any medical condition.

Exclusion criteria:

- Patients with medical conditions that may affect periodontal healing or regeneration.
- Patients with a history of allergic reactions, pregnant or breastfeeding females,
 smokers and alcoholics
- Patients with current or previous drugs intake that may predispose to gingival enlargement.
- Patients under orthodontic treatment or had orthodontic treatment in the past six months.
- Carious teeth, proximal restorations or fixed prosthesis.
- Patients with a history of traumatic oral hygiene measures or periodontal surgeries over the last six months at the area of interest or having any scar tissue.
- Poor oral hygiene patients.

11. Interventions

11a-General operative procedure

- The patients who fulfil the inclusion criteria will be enrolled.
- The nature of the study will be explained to each patient as well as the importance of compliance with pre- and post-operative instructions and follow-up visits.
- Each patient will be asked to sign an informed consent (appendix 1)
- After enrolment, periodontal examination and full periodontal charts will be recorded for each patient including Papilla Class I1, CP-BC plaque Index (*Leary et al., 1967*), gingival bleeding Index (*Ainamo & Bay, 1975*), probing depth (PD), clinical attachment level (CAL) and gingival recession.

Radiographic Evaluation

Standardized digital periapical radiographs will be obtained preoperatively and at follow-up using the long cone paralleling technique. All radiographs will be obtained using the same equipment, film exposure and development conditions.

Pre-surgical therapy

- All patient will receive strict oral hygiene instructions full mouth supra and sub-gingival debridement using hand instruments and ultrasonic scalers under local anesthesia.
- Four to six weeks following pre-surgical therapy, a periodontal re-evaluation will be performed to confirm the suitability of the chosen sites for this periodontal surgical study.
- The clinical and radiographic parameters will be recorded at baseline

The patients will be randomly assigned into two groups: A total of 36 sites (18 site per group)

Group A (Intervention): Patients will receive Tube technique.

Group B (Control): Patients will receive Hyaluronic acid.

Surgical Procedures

Group A (Intervention): Patients will receive Tube technique (Hooshang et al. 2020).

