- 8) The size of the needle does not matter for this procedure; we use 4-0 silk with an FS2 cutting needle and a 4-0 chromic gut suture with a C-6 (FS-2) cutting needle.
- 9) Using the index finger and thumb the graft will be squeezed from both ends inward for at least 4 to 5 minutes to further stabilize the graft into position. Both patients are instructed to avoid

brushing or flossing the recipient as well as donor site. They are also asked to avoid hot, chewy, sticky foods. They were advised to ice the wound to reduce post-surgical swelling.

Group B (Control): Patients will receive Hyaluronic acid (HA) (0.1) mm (*Abdelraouf etal. 2019*) The product used in this trial is Restylane Lidocaine (Restylane-Lidocaine cross-linked Hyaluronic Acid Filler, Galderma S.A, Sweden). Restylane was the first FDA-approved HA filler in 2003. Restylane is a non-animal stabilised cross-linked HA filler with an HA concentration of 20 mg/ml. The longevity of Restylane filler in tissues is approximately 6 months. Restylane-Lidocaine (FDA approved in 2012) is a newer product of Restylane with 0.3% lidocaine incorporated into the syringe itself.

- -Stent will be performed and re evaluation
- -After 4 weeks, re-evaluation is performed, and the degree of papillary deficiency according to *Nordland and Tarnow* 1998 classification as well as plaque and gingival indices will be assessed for eligibility. Alginate impression is taken for the involved arch/arches for the construction of study casts and fabrication of customized stents. Only patients with deficient papilla sites fulfilling the inclusion criteria are recalled, scheduled for the 1st injection after 1 week and will sign the informed consent.

After 1 week 3 injection will be given at each papilla site

- -In the injection phase, 3 injections are given at each papilla site: at baseline, 3- and 6-weeks intervals. At the first injection visit, before attempting to inject, clinical measurement of the height of the black triangle is done by measuring the distance between the deficient papilla tip and contact area (PT-CP distance) to the nearest 0.5 mm (baseline). This will be done using a graduated periodontal probe and the fabricated customized stent for proper and standardized positioning of the probe at each measurement interval

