This power analysis used interdental papilla loss after six months as the primary outcome. Based upon the results of Awartani FA and Tatakis DN (2016), the mean and standard deviation (SD) for control group were 0.71 (0.74) mm2. The minimal clinically significant difference was 1 mm2according to expert opinion. Using alpha (α) level of (5%), β level of 0.8 (Power = 80%); the effect size for independent samples t-test (d) was 1.32 and the minimum estimated sample size was 10 sites per group. Sample size was increased to 12 sites per group to compensate for a drop-out rate of 20% after six months. Sample size calculation was performed using PS Power and Sample Size Calculations Version 3.

15. Recruitment strategy

- The main investigator will be responsible for recruitment of patients.
- Patients will be selected from the outpatient clinic of the Oral Medicine and Periodontology
 Department, Faculty of Dentistry Cairo University.
- Screening of patients will continue until the target sample is achieved.
- Identifying and recruiting potential subjects will be achieved through patient database.
- 1. One year.
- 2. Candidate self-funding

B) Assignment of interventions

16. Allocation

16a. Randomization

The patients will be randomly allocated to either the intervention group or the control group using computer generated random numbers that will be performed by the supervisor. The patients will be allocated in a ratio of 1:1.

16b. Allocation concealment mechanism

The two groups will be equally prepared for both surgical procedures. Then the decision of which group will receive Hyaluronic acid injection and which will Tube Technique will be taken according to the randomized numbers placed in opaque sealed envelopes. The number will be picked by the supervisor.

16c. Implementation

The supervisor will be responsible for generation of allocation sequence as will as assign the patients to the 2 intervention groups. The main investigator will be responsible for patient enrollment.

17. Masking/blinding:

Due to the type of intervention only the outcome assessor and the statistician will be blinded. Single blinded:

- Blinding of the participants is not applicable.
- Blinding of the operator is not applicable.
- Outcome assessor (primary and secondary outcomes) and biostatistician will be blinded.

Key elements of Random Sequence Generation in protocol are:

- 1-Method of random sequence generation (computerized random number generator).

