- 2- Allocation ratio (1:1, 2:1).
- 3- Type of randomization: simple, blocked, stratified.

c) Data collection, management, and analysis:

18. Data collection methods

- All the data of the patients included in the study will be recorded from them or extracted from the patient's periodontal chart.

- Telephone numbers of all patients included in the study will be recorded as a part of the written consent.
- All patients will receive a phone call at the time of the pre-determined follow up dates.

19. Data management:

Excel sheet program will be used though a computer system to manage the data with a secured password.

20. Statistical methods:

- The outcome used (State 1ry or 2ry): interdental papilla loss area (mm2)
- Values used for outcome (e.g. mean difference, percentage, proportion..... etc): mean and standard deviation
- Entry 1: (mean difference between 2 groups, mean and standard deviation of group 1, proportion 1 or estimated prevalence):

Minimal clinically significant difference = 1 mm2 according to expert opinion

• Entry 2: (standard deviation of control group, mean and standard deviation of group 2, proportion 2 or clinically important difference):

Mean of the control group = 0.71

SD of control group = 0.74

- Alpha level of significance: 0.05
- Effect size used in calculation: d = 1.32
- Power of the study: 0.8
- Statistical test used: Independent samples t-test
- The calculated sample size: 10 sites per group.
- Increased number for anticipated missing data: Sample size will be increased to 12 sites per group to compensate for a drop-out rate of 20% after six months.

D) Data monitoring:

21. Monitoring

No formal data monitoring committee will be needed since it is a study with known minimal risks.

22. Harms

Postoperative pain and/or swelling will be managed through analgesics.

23. Audit

Auditing of the study design will be done by the evidence-based committee – Faculty

Dentistry – Cairo University.

IV. Ethics and dissemination

24. Research ethics approval

This protocol and the template informed consent form will be reviewed by the Ethics Committee of Scientific Research -Faculty of Dentistry- Cairo University.

25. Protocol amendments

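### Patients are randomised, but the sample size and recruitment target are counted in sites, with no limit of one site per patient and no allowance for clustering

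*Protocol*

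**What the plan says.** Protocol section 16a makes the patient the unit of randomisation: "The patients will be randomly allocated to either the intervention group or the control group using computer generated random numbers". Every size target is in sites:

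- Section 14 gives the calculation: "the effect size for independent samples t-test (d) was 1.32 and the minimum estimated sample size was 10 sites per group". It then raises this to 12 sites per group for 20% drop-out, and section 20 repeats both figures.
- Section 11a, at the assignment to groups, gives a different total: "A total of 36 sites (18 site per group".
- No section gives a number of patients.

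More than one site per patient is permitted. The inclusion criteria (section 10) admit patients "having at least one deficient papilla in the anterior region", with no maximum. In the Group B description (section 11), "3 injections are given at each papilla site". Section 15 adds: "Screening of patients will continue until the target sample is achieved".

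The one test named is in section 20: "Statistical test used: Independent samples t-test". The protocol mentions no index papilla, patient-level summary, ICC or design effect.

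**The concern.** Papillae in one mouth share the patient's tissue type, oral hygiene and healing, and here they also share the allocated treatment. Their outcomes are therefore likely to be positively correlated, and two sites in one patient carry less information about the treatment than two sites in two patients.

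Because recruitment runs until a target in sites is reached, each patient with several papillae reduces the number of independently randomised units. Two things are then at stake. A t-test on sites understates the standard error and gives too many false positives. The stated 80% power also exceeds what an analysis respecting the randomisation can deliver. Whatever analysis is chosen, the number of patients to randomise cannot be worked out from the document.

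**Working it through.** **Inputs from the protocol (sections 14 and 20).** Difference 1 mm²; control SD 0.74 mm²; d = 1.32; power 80%; independent-samples t-test; "Alpha level of significance: 0.05". Sidedness is not stated. Two-sided is assumed, since a one-sided exact t calculation gives 8 per group, not 10.

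**Assumed, because the protocol does not give them.** Sites per patient m, and ICC of 0.3, 0.5 and 0.7, with 0.1 as a mild case. Results are listed in the order 0.3/0.5/0.7.

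**Step 1: reproduce the plan's figure.** By the normal approximation, n = 2 × (1.960 + 0.842)² / 1.32² = 9.01, rounded up to 10 per group. By the exact noncentral t, 10 per group gives 79.7% power at d = 1.32. The protocol's own inputs give d = 1/0.74 = 1.35, and power is then 81.5%. Adding 20% to 10 gives 12. The figure reproduces only if all sites are independent.

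**Step 2: power of a valid analysis with k patients of m sites per group.** The SD of a patient mean is 0.74 × √[(1 + (m − 1) × ICC)/m]. Power follows from a noncentral t with 2k − 2 degrees of freedom and noncentrality (1/SD of mean) × √(k/2).

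Example with k = 5, m = 2, ICC 0.5: SD of mean = 0.74 × √(1.5/2) = 0.641; noncentrality = (1/0.641) × √2.5 = 2.47; 8 degrees of freedom; power 58%.

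**Step 3: type I error of a t-test on sites.** Simulation of 60,000 trials per scenario, two-level normal data, the same site pattern in both groups, two-sided 5%. Power for unequal patterns was also simulated.

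| Sites per group | Pattern per group | Type I error, site-level t-test | Power, patient-mean t-test |
|---|---|---|---|
| 10 | 10 patients × 1 | 5% | 81.5% |
| 10 | 6 × 1 plus 2 × 2 | 6.4/7.4/8.5% | 75/74/72% |
| 10 | 5 × 2 | 9.0/11.7/15.0% | 64/58/53% |
| 12 | 8 × 1 plus 2 × 2 | 6.1/7.2/7.8% | 84/83/83% |
| 12 | 6 × 2 | 8.8/11.5/14.6% | 74/68/63% |
| 12 | 4 × 3 | 12.7/18.1/23.6% | 59/50/44% |
| 18 | 9 × 2 | 8.7/11.3/14.0% | 92/87/83% |
| 18 | 6 × 3 | 12.7/17.7/22.7% | 82/73/66% |

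The patient-mean t-test kept its type I error between 4.8% and 5.2% throughout.

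**Step 4: mild cases.** With 12 sites and a single two-site patient per group, site-level type I error is 5.7/6.0/6.4%. At ICC 0.1, the 6 × 2 pattern gives 6.1% type I error and 81% patient-level power.

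**Step 5: size needed with two sites per patient.** The smallest k reaching 80% is 7 (82.1%), 8 (82.7%) or 9 (83.1%) patients per group. That is 14, 16 or 18 sites instead of 10.

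**The case against.** The strongest reply is that one site per patient may be what is meant. The CP-BC and probing-depth criterion and the photography section speak of the deficient site or papilla in the singular, and the surgical description covers one recipient tunnel and one graft. The drop-out rate is also applied directly to sites, which is natural if a site is a patient. Requiring one or more deficient papillae is an entry threshold; it does not say that all of them are treated or analysed. If one site is meant, there is no statistical harm.

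Second, the t-test is listed among the sample-size entries, so it may not be the planned primary analysis. A t-test on patient means is also an independent-samples t-test, and a separate analysis plan could fix the unit of analysis.

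Third, both m and the ICC are assumed, and the largest figures need every patient to contribute two or three sites with substantial correlation. With two two-site patients among 12 sites per group, power stays above 80%. With the same two among 18 sites, type I error is about 6% to 7% and power about 96%.

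These points limit the size of the problem and make it conditional. They do not remove it. The singular wording is not a rule, and the control-arm text also refers to sites and black triangles in the plural. An analysis plan could choose a clustered analysis, but it could not repair a recruitment target fixed here in a unit other than the one randomised.

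**Conclusion.** The concern holds, conditionally on patients contributing more than one papilla, which the protocol permits and does nothing to limit. With one site per patient, the 5% error rate and the 80% power stand.

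With more than one site and any positive ICC, a site-level t-test exceeds 5% and the power claimed for 10 sites is overstated. The size runs from slight (about 6% type I error for one two-site patient among 12 sites per group) to serious (9% to 15% type I error and 53% to 64% valid power if all patients give two sites at 10 sites per group). The 18-site total in section 11a would keep power above 80% with two sites each, but would not protect the error rate of a site-level test.

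These figures rest on the protocol's SD and difference and on assumed ICCs of 0.3 to 0.7. Independently of those assumptions, the number of patients to randomise is undefined. This should be corrected before enrolment, because independent patients not recruited cannot be recovered at analysis.

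**What to change.** 1. Make the patient the unit of the primary analysis, preferably by naming one index papilla per patient before randomisation.
2. If several papillae per patient are to count, state the maximum number. Analyse patient means, or use a mixed model with a random patient effect and a small-sample degrees-of-freedom correction such as Kenward-Roger. The two approaches coincide only when all patients have the same number of sites.
3. State the target in patients in sections 11a, 14, 15 and 20, apply the drop-out allowance to patients, and reconcile the 12 and 18 per group.
4. State that the 80% power refers to 10 evaluable patients per group with one site each. If several sites are intended, give the lower power or the larger number, with the assumed ICC.

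If one site per patient is intended, the cost is one or two sentences. If several are intended, the stated power becomes less favourable or more patients are needed: with two sites each, 7 to 9 evaluable patients (14 to 18 sites) per group under the ICCs used here. No additional measurements are required.

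### Twelve sites per group do not cover the stated 20% drop-out from a minimum of 10; they cover 2 of 12 (16.7%). The effect is small and arises only if 12, not 18, is the enrolment target

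*Protocol*

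**What the plan says.** Section 14 (Sample size) bases the calculation on black-triangle area at six months and concludes that "the minimum estimated sample size was 10 sites per group". The next sentence reads "Sample size was increased to 12 sites per group to compensate for a drop-out rate of 20% after six months". Section 20 (Statistical methods) repeats the same base of 10 and the same allowance: "Sample size will be increased to 12 sites per group to compensate for a drop-out rate of 20% after six months".

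The inputs given for the 10 are:
- "Alpha level of significance: 0.05";
- power of 80%;
- "Statistical test used: Independent samples t-test";
- "The minimal clinically significant difference was 1 mm2according to expert opinion";
- "SD of control group = 0.74";
- an effect size of 1.32.

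Section 11 (Interventions, under pre-surgical therapy) gives a different enrolment figure: 36 sites, 18 per group. It offers no derivation and does not mention the 12.

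**The concern.** A drop-out allowance should leave the required number once the expected fraction has been lost. To do that, the required number is divided by the fraction retained. Adding the drop-out percentage to the required number always falls short, because the loss then applies to the enlarged number. The figure of 12 looks like the second method.

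If so, the sentence that justifies the enrolment number claims a protection that the number does not give. The error stands in both places where the protocol justifies its sample size. Section 15 continues screening until the target sample is reached, so the number written as the target decides when recruitment ends. If withdrawals ran at the rate the protocol expects, the six-month comparison would be made on fewer sites than its stated minimum.

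**Working it through.** **Inputs.** Alpha 0.05, power 0.80, difference 1 mm², SD 0.74 mm², effect size d = 1.32, minimum 10 per group, drop-out 20% and inflated figure 12 are all from Sections 14 and 20. Allocation is 1:1 (Section 16a). The protocol does not say whether the test is one- or two-sided. Two-sided is assumed because it reproduces the 10; the one-sided normal approximation gives 8. The stated d is slightly below 1/0.74 = 1.35, so both values are carried through.

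**Step 1: reproduce the base of 10.** n per group = 2(1.960 + 0.842)²/d².
- With d = 1.32: 2 x 7.85/1.742 = 9.01, rounded up to 10.
- Check by the noncentral t distribution at 10 per group: power is 79.7% with d = 1.32 and 81.5% with d = 1/0.74.

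The 10 is therefore reproduced, with almost no slack at the stated d.

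**Step 2: reproduce the 12.** 10 x (1 + 0.20) = 12. This is the protocol's figure.

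**Step 3: apply the stated loss.**
- Retained from 12: 12 x (1 - 0.20) = 9.6, below 10.
- Largest loss that still leaves 10: 2 of 12 = 16.7%.
- Number needed to keep 10: 10/(1 - 0.20) = 12.5, so 13. Check: 13 x 0.8 = 10.4.
- On the total: 20/0.8 = 25, against 24 stated; equal groups make it 26.

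**Step 4: size of the effect.** Power of the two-sided t-test at alpha 0.05, with noncentrality d√(n/2) and 2n - 2 degrees of freedom. The value at 9.6 treats n as continuous.

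| Sites per group analysed | d = 1.32 | d = 1/0.74 |
|---|---|---|
| 12 (no loss) | 87.1% | 88.5% |
| 10 (stated minimum) | 79.7% | 81.5% |
| 9.6 (20% lost from 12) | 77.9% | 79.7% |
| 9 (3 of 12 lost) | 74.8% | 76.8% |

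The expected cost of the shortfall is 79.7 - 77.9 = 1.8 percentage points, or 81.5 - 79.7 = 1.8 with the other effect size. If 5 of the 24 sites are lost and the groups end at 10 and 9, power is 77.3% or 79.2% (d = 1/0.74).

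**Step 5: the Section 11 figure.** 18 x 0.8 = 14.4 sites per group. At d = 1.32, power is 91.9% at 14 and 93.7% at 15, so about 93% at 14.4. With that target the shortfall does not arise.

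**The case against.** The strongest reply is that this is one site per group. Sites are lost whole: 20% of 12 is 2.4, and a loss of 2 leaves exactly 10. If the 20% is read as a share of the required 10, the 12 even fits. The difference of about 2 power points is also well within the uncertainty of a difference set by expert opinion and an SD from a single cited study. All of this stands as a comment on size. It does not rescue the sentence: a drop-out rate is ordinarily a share of those enrolled, and a loss of 2 of 12 is 16.7%.

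A second reply is that the real target may be 18 per group. This also stands, and it makes the consequence conditional. It leaves the statement about 12 uncorrected in both sections.

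A reader might infer that the allowance is what makes the trial miss its 80% power. The figures do not support that. At d = 1.32, power is already 79.7% at 10 per group with no loss at all. With d = 1/0.74, it is the same 79.7% at 9.6 per group.

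A reader might also judge the allowance by the chance that both groups keep at least 10 sites. Suppose each site is lost independently with probability 0.20, which is an assumption. That chance is then 0.31 with 12 per group and 0.56 with 13. The protocol sets no such criterion, and 13 would not guarantee it either. Independence is also doubtful: patients are randomised (Section 16a) and may have more than one deficient papilla (Section 10), so one withdrawal could remove several sites.

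**Conclusion.** The point holds as an arithmetic error of small effect. On the protocol's own inputs, 12 per group does not compensate for a 20% drop-out from a minimum of 10: it leaves 9.6 and tolerates at most 16.7%. The correct inflation gives 13.

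If 12 is enrolled and 20% are lost, expected power is 77.9% at the stated effect size, or 79.7% at 1/0.74. If a whole third site is lost from each group, it is 74.8% or 76.8%. If 18 per group is enrolled, there is no shortfall and only the sentence is wrong. The power figures assume a two-sided test, and treat the sites as independent, as the protocol's t-test does. The shortfall itself needs neither assumption. The documents do not support a reading that the trial is materially underpowered because of this allowance. The unexplained difference between 12 and 18 is the larger sample-size problem.

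**What to change.** Correct the allowance in Sections 14 and 20 in one of two ways.

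1. Keep 12 and state what it covers, for example: *Twelve sites per group allow for the loss of up to 2 of 12 (16.7%). At a 20% loss about 9 to 10 sites per group remain, and power is about 75 to 80% at an effect size of 1.32.*
2. Keep 20% and give the correctly inflated number: *10/0.8 = 12.5, rounded up to 13 sites per group.*

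In the same edit, reconcile this number with the 18 per group in Section 11, so that one enrolment target with one derivation appears throughout. State there that the test is two-sided, if it is.

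The cost is one sentence in two sections plus the reconciliation. The first option needs no extra patients but makes the stated allowance slightly less favourable. The second adds one site per group, 26 in total against 24. Section 25 lists sample size among the changes that need a formal amendment, so any change to the number should be made through that route.
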